	
 
• Effect on hepcidin and iron metabolism
 
• Effect on cholesterol and lipid parameters
 
 
Additional Exploratory Efficacy Endpoints: Additional exploratory efficacy endpoints are described in the statistical analysis plan and will use the Full Analysis Set (FAS) population.

Safety Assessments:	
 
• Adverse events (AE) and serious adverse events (SAEs) reporting
 
• N (%) patients with progression to acute myeloid leukemia (AML)
 
• Clinical laboratory measures, including hemoglobin and liver function tests (LFTs) (AST, ALT, total bilirubin (TBili) and alkaline phosphatase(ALP))
 
• Heart rate, blood pressure and electrocardiogram (ECG)
 

PK/PD Biomarkers & Other Labs:	
 
• Measurements of PK, serum erythropoietin levels
 
• Measurements of iron indices including serum iron, ferritin, transferrin or total iron binding capacity (TIBC), saturation and hepcidin
 
• Measurements of lipids/cholesterol levels
 

Statistical Methods:	
Data from patients in the OL component will be analyzed separately from the DB randomized component of the study.
 
DB Component: Descriptive statistics including number of patients (N), means, standard deviations, medians, and minimum and maximum values will be presented for continuous variables. Counts and percentages will be presented for categorical variables. For efficacy endpoints, the standard error and 95% confidence intervals will be presented as part of the descriptive summaries.
 
The following analysis sets are defined and will be used for the statistical analysis:
 
 
• Full Analysis Set (FAS)
 
• Safety Analysis Set (SAF)
 
 
The FAS Population consists of all patients randomized to the study. This is the population used for the efficacy analyses.
 
The Safety Population consists of all patients who have received at least one dose of study drug.
 
Analyses of the safety data will be based on the Safety Populations.
 
Baseline Hb value for efficacy analysis is defined as the mean of Screening central laboratory Hb value and Day 1 Hb value.


Statistical Methods (cont.):
	
Data Analyses
 
160 patients will to be randomized in a 3:2 ratio to roxadustat or matching placebo. This sample size will provide at least 90% power to demonstrate a statistically significant difference between roxadustat and placebo at the significance level of 0.05 using a two-sided Fisher's test, and assuming the response rates of the primary endpoint are 35% and 5% in roxadustat and placebo, respectively.
 
The primary endpoint of the study will be compared between the two treatment groups using the Cochran-Mantel-Haenszel (CMH) chi-square test, controlling for stratification factors.
 
If one or more of the levels of the stratification variables are underrepresented during enrollment resulting one or more of the (2×2×2) 8 strata having with too few patients to meet the required per-strata sample size for the planned statistical methodology then the stratification variable with the highest imbalance will not be included in the analysis. This practice will be followed for the primary, secondary and exploratory variables.
 
Categorical endpoints will be analyzed using the CMH test.
 
Cox regression model will be used to analyze time-to-event endpoints. Analyses will be adjusted by stratification factors and baseline value if applicable.
 
A sequential gate keeping procedure will be used to control the family-wise type I error rate in multiple testing of the primary and secondary efficacy endpoints.
 
Summary of safety data will be based on the Safety Population. Safety parameters include adverse events, laboratory parameters, progression to AML, vital signs, ECG parameters, prior and concomitant medication use.
 
Data Safety Monitoring Board (DSMB):
 
A Data Safety Monitoring Board (DSMB) will be established prior to the start of the DB portion of the study and will oversee the study on a regular and pre-defined basis. The role and function of the DSMB will be defined in the DSMB charter. Of particular note, the likely initial starting dose for the study is 2.0 mg/kg. This may be adjusted in agreement with the DSMB if supported by-data review.

--	--

This study will be conducted in accordance with the guidelines of Good Clinical Practice and the applicable regulatory requirement(s), including the archiving of essential documents.

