
Study Design Overview (cont.):
	
weeks. A primary efficacy assessment will be made in the DB component when all randomised patients have completed 28 weeks DB treatment or have discontinued.
 
Unless indicated, the same procedures will apply in both components of the study.
 
In the OL lead-in component, up to 24 patients will be enrolled in sequential dose level cohorts (n=8) prior to the start of the DB portion of the study. All patients will receive roxadustat in an OL manner. The first 8 patients will receive a starting dose of 1.5 mg/kg. The next 8 patients will receive a starting dose of 2.0 mg/kg. The last 8 patients will receive a starting dose of 2.5 mg/kg. The roxadustat dose per body weight are estimates only and the exact dose will be assigned per body weight ranges as shown in the body of the protocol.
 
Upon enrolling the OL component of the study, approximately 160 patients will be randomized in the DB placebo controlled portion of the study.
 
Screening Period:
 
All screening procedures are to be completed within 28 days prior to Day 1 of Treatment, except for documentation of the following which can be obtained from patients' medical records:
 
 
1. Lower risk MDS (IPSS-R very low risk, lower risk, or intermediate risk). There is no minimum time from diagnosis to registration/randomization except to allow for proper IPSS-R classification to be made, and to show transfusion dependence for patients in both portions of the study.
 
2. Results from bone marrow examination and cytogenetic analysis performed within 16 weeks prior to Day 1 of treatment can be used. The required bone marrow slides and report must be available for a centralized review at any time throughout the study.
 
3. Patients are deemed to have low RBC transfusion burden (LTB) if they received 1 to 4 documented pRBC transfusions within 8 weeks prior to registration/randomization. Patients with 1 pRBC/8-weeks must have a documented history of requiring 1 pRBC/8-weeks in 2 consecutive periods of 8 weeks in the 16 weeks preceding registration/randomization. Pre-transfusion and post-transfusion hemoglobin (Hb) levels within 8 weeks prior to Day 1 of treatment will also be recorded. The percentage of patients having 1pRBC transfusion at baseline will be capped at 30% for the DB portion of the study.
 
 
Open-Label patients only, the requirement to demonstrate

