--	---

Study Design Overview (cont.):
	
transfusion dependence can also be met by a principal investigator (PI) starting this particular patient on pRBC transfusion during the screening period.
 
Patients must meet all inclusion and none of the exclusion criteria to be eligible for the OL or the DB components of the study.
 
Treatment:
 
Up to 24 patients will be enrolled in sequential dose level cohorts prior to start of the DB portion of the study. All patients will receive roxadustat in an OL manner. The first 8 patients will receive a starting dose of 1.5 mg/kg (Dose Level 1). The next 8 patients will receive a starting dose of 2.0 mg/kg (Dose Level 2). The last 8 patients will receive a starting dose of 2.5 mg/kg (Dose Level 3).
 
The starting dose table for the OL component of the study is shown below.
 
  
 Dose Level Group	Approximate Roxadustat dose level ( mg/kg)	Patient Weight	
 
 45 to <70 kg	70 - 100 kg	> 100 kg	
   
 1	1.5	70 mg TIW	120 mg TIW	150 mg TIW	
 
 2	2.0	100 mg TIW	150 mg TIW	200 mg TIW	
 
 3	2.5	150 mg TIW	200 mg TIW	250 mg TIW	
  
 
The OL is intended to optimize the starting dose for the subsequent DB portion of the study in which, 160 eligible lower risk MDS patients with LTB will be randomized 3:2 to roxadustat or matching placebo. It is anticipated that the starting dose level will be Dose Level 2 (2.0 mg/kg) and the protocol is written to reflect this but if the OL data identifies Dose Level 1 or 3 as a more optimal starting dose, this will be implemented.
 
Patients in the DB component of the study will be randomized with the following stratifications:
 
 
• Serum erythropoietin (EPO) level: either <math>\leq 200</math> mIU/mL OR <math>> 200</math> mIU/mL and <math>\leq 400</math> mIU/mL
 
• IPSS-R low risk /very low risk vs. intermediate risk group classification
 
• RBC transfusion burden: 1 pRBC/8-weeks over 16 consecutive weeks vs 2-4 pRBC/8-weeks
 
 
The PI and site staff will utilize their own institutional criteria for the determination of when to transfuse a patient. Documentation of
	Dose Level Group	Approximate Roxadustat dose level ( mg/kg)	Patient Weight			45 to <70 kg	70 - 100 kg	> 100 kg	1	1.5	70 mg TIW	120 mg TIW	150 mg TIW	2	2.0	100 mg TIW	150 mg TIW	200 mg TIW	3	2.5	150 mg TIW	200 mg TIW	250 mg TIW

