### 8.2 Randomization and Treatment Assignment

Patients will be randomized, stratifying by the following

- Serum EPO level: either  $\leq 200$  mIU/mL OR  $> 200$  mIU/mL and  $\leq 400$  mIU/mL
- IPSS-R low risk / very low risk vs. intermediate risk group classification
- RBC transfusion burden: 1 pRBC/8-weeks documented over 16 consecutive weeks vs 2-4 pRBC documented over 8 weeks. NOTE: 1-pRBC randomization will be limited to no more than 30% of the total randomized patient population

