5.6. Randomization Errors

Patients who were randomized from an incorrect stratum will be identified by comparing the strata recorded on the RTSM system (Randomization and Trial Supply Management)/randomization CRF page with the strata derived from screening data. A listing of patients who were randomized from an incorrect stratum will be presented. The randomized stratum (from RTSM system/randomization CRF) rather than actual stratum (derived from screening data) will be used for all the efficacy analyses. A sensitivity analysis will be performed using the actual stratum on the primary endpoint if the discrepancy rate is greater than 5% in the final result.

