The null and alternative hypotheses that will be tested at 2-sided significant level 5% are:

H_0 : OR = 1 versus H_a : OR \neq 1

The p-value from the stratified CMH chi-square test will be the confirmatory p-value for the test of the null hypothesis that the proportion of patients achieving RBC transfusion independence is equal between the two treatment groups.

SAS code for Cochran-Mantel-Haenszel (CMH) test

The two-sided CMH test will be performed using SAS procedure PROC FREQ with the CMH option in the TABLES statement. Baseline EPO level, IPSS-R risk category and RBC transfusion burden will be the stratification variables. The variables <reatment> and <response> determine the rows and columns of the tables.

Sample code:

```
PROC FREQ DATA = <input_dataset sorted> NOPRINT;  
    TABLES <strata_var>* <treatment_var> * <response_var> / CMH EXACT RISKDIFF;  
RUN;
```

Handling of missing values in primary analysis

Patients who have discontinued treatment early for any reasons prior to week 8 will be classified as non-responders. If significant differential treatment discontinuation prior to week 8 is observed between the two treatment groups, additional sensitivity analyses may be explored.

Sensitivity Analysis

Sensitivity Analysis 1: PPS Analysis

The primary analysis will be repeated using PPS as a sensitivity analysis.

Sensitivity Analysis 2: Logistic Regression Analysis

The primary analysis for primary endpoint will also be repeated using a multivariate logistic regression. The following variables/factors will be used in the model:

- treatment group (roxadustat vs. placebo);
- age group (< 65 vs. ≥65 years);
- centrally confirmed IPSS-R category (Intermediate vs. Low-risk/very low risk);
- transfusion burden (1 pRBC/8-weeks over 16 consecutive weeks vs. 2-4 pRBC/8-weeks);
- baseline hemoglobin
- baseline EPO level (≤200 mIU/mL vs. >200 mIU/mL and ≤400 mIU/mL);

In addition, MDS duration, baseline platelet counts, and bone marrow blasts will be also investigated as continuous variables.

A Wald test based on the estimated regression parameter for treatment group assignment will provide the basis for the hypothesis testing. The odds ratio (roxadustat versus placebo) and its 95% confidence interval will be provided. An example of the SAS code is displayed below:

```
PROC LOGISTIC;  
    CLASS <treatment_var> <factors>;  
    MODEL <response_var> = <treatment_var> <factors>;  
RUN;
```

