The exposure time will be measured using patient-exposure-week (PEW). PEW of TI periods over the first 28-weeks will be added up to a cumulative number of weeks. For a patient with at least one TI response period over the first 28-weeks, the last TI response period will end with the date of a subsequent RBC transfusion, visit date at week 28, date of the end of study or treatment discontinuation due to AE/SAE or death, whichever comes earlier. For a patient with no TI response period over the first 28 weeks, the cumulative number of PEW will be set to zero.

The cumulative number of PEW over the first 28 weeks of treatment period will be summarized using descriptive statistics by treatment group. Treatment comparison will be based on a non-parametric ANCOVA (stratified rank ANCOVA) described in Stokes, Davis, and Koch 2000. The analysis will use baseline hemoglobin as covariate, treatment arm as fixed effects, controlling for stratification factors (baseline endogenous EPO level, IPSS-R risk category and RBC transfusion burden). See [Section 5.5](#) for the definition of number of pRBC (packs of red blood cells) transfusions at baseline.

Since it is expected that the sample sizes are not large for all strata, the following steps and SAS codes are to be used:

Step 1: Compute the ranks of the response variable and covariate across the two treatment groups.

Sample SAS code:

```
PROC RANK TIES = mean OUT = ranks;  
  BY <strata_var>;  
  VAR <baseline_var> <response_var>;  
RUN;
```

Step 2: With the ranks of response variable, an ANCOVA model will be fitted including the baseline ranks and stratification factor as covariates.

Sample SAS code:

```
PROC MIXED DATA = ranks;
  CLASS <strata_var>;
  MODEL <R_response_var> = <R_Baseline_var> <strata_var>/OUTP = res;
RUN;
```

Step 3: CMH mean score statistics will be used to compare the two treatment groups using the values of the residuals obtained from step 2 as scores. The p-value obtained will be reported.

Sample SAS code:

```
PROC FREQ DATA = res;
  TABLES <strata_var>* <treatment_var>*resid/CMH2;
RUN;
```

The p-value from the stratified CMH chi-square will be provided for the test of the null hypothesis that there is no difference in two treatment groups.

Week 28 and week 52 are the analysis endpoint for 28-week and 52-week analysis respectively.

This analysis will take into account the potential intercurrent events as follows:

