1. Treatment discontinuation (such as: due to Disease progression, Liver function, Patient decision, Investigator decision, AE/SAE, etc.): using While on treatment strategy: PEW of TI will be estimated in the duration beginning with the first dose date (Day 1) and ending with the date of end of treatment or last visit date at week 28/52, whichever comes earlier.
2. Death: using While on treatment strategy: Treatment effect while on-treatments of interest. PEW of TI will be based on RBC transfusion records up to the date of end of treatment or last visit date at week 28/52 or death, whichever comes earlier.

In addition, the cumulative number of Patient-Exposure-Weeks of TI at week 28 and week 52 will be also summarized using the box-whisker plot by treatment groups.

12.3.3.4. Number of pRBC Transfused compared to Baseline over the first 28 Weeks of the Treatment Period

Descriptive statistics of the number (pRBC/8 weeks) of pRBC transfused and number (pRBC/8 weeks) of pRBC transfused change from baseline will be presented by treatment group using FAS and PPS. See [Section 5.5](#) for the definition of number of pRBC transfusions at baseline.

Treatment comparison will be performed for the number (pRBC/8 weeks) of pRBC transfused change from baseline based on a non-parametric ANCOVA (stratified rank ANCOVA) using baseline hemoglobin and baseline pRBC transfusions (pRBC/8 weeks) as covariate, treatment arm as fixed effects, controlling for stratification factors baseline endogenous EPO level and IPSS-R risk category. The p-value obtained will be reported for the test of the null hypothesis that there is no difference in two treatment groups.

Week 28 and week 52 are the analysis endpoint for 28-week and 52-week analysis respectively.

Similar methods will be used as in [Section 12.3.3.3](#). Similar Strategies will be implemented for potential intercurrent events.

12.3.3.5. Proportion of Patients Who Achieved TI for ≥ 20 consecutive Weeks (140 consecutive Days) anytime during the study

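### Optional precision gain: Test 5 and the logistic check on the primary endpoint use transfusion burden only as 1 vs 2-4 units, although each patient's baseline count is already derived

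*Protocol*

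**What the plan says.** - **The split.** The Protocol Synopsis defines the third stratification factor as "RBC transfusion burden: 1 pRBC/8-weeks over 16 consecutive weeks vs 2-4 pRBC/8-weeks". Protocol 8.2 adds that "1-pRBC randomization will be limited to no more than 30% of the total randomized patient population". SAP 3.3 repeats both.
- **Which value is used.** SAP 5.6: "The randomized stratum (from RTSM system/randomization CRF) rather than actual stratum (derived from screening data) will be used for all the efficacy analyses". Where an efficacy model controls for burden as a stratification factor, it therefore uses the two-level randomized value.
- **Test 5 (SAP 12.3.3.3).** A stratified rank ANCOVA: "The analysis will use baseline hemoglobin as covariate, treatment arm as fixed effects, controlling for stratification factors". The next sentence refers the reader to SAP 5.5 for the baseline number of pRBC transfusions, but no term in the stated model uses that number.
- **Test 6 (SAP 12.3.3.4).** The same type of model, "using baseline hemoglobin and baseline pRBC transfusions (pRBC/8 weeks) as covariate". Here the stratification factors are EPO level and IPSS-R only; the burden stratum is dropped.
- **Sensitivity Analysis 2 (SAP 12.3.1.1).** A logistic model for the primary endpoint that lists "transfusion burden (1 pRBC/8-weeks over 16 consecutive weeks vs. 2-4 pRBC/8-weeks" as a factor. It then says that "MDS duration, baseline platelet counts, and bone marrow blasts will be also investigated as continuous variables". The baseline pRBC count is not among these.
- **Availability of the count.** Protocol 6.1 has transfusions over the 16 weeks before Day 1 recorded for every patient. SAP 5.5 turns them into a count per 8 weeks: half the 16-week total, or the 8-week total where only that is available.

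**The concern.** The endpoint needs 56 days without a transfusion. If single units are given at even intervals, a patient on 2 units per 8 weeks is transfused every 56/2 = 28 days and one on 4 units every 56/4 = 14 days. The first must double the interval to respond; the second must quadruple it. Both analyses treat these two patients as alike, and stratified randomization does not balance 2 against 3 against 4 units within the 2-4 level.

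Two things are at stake. Test 5 is a gatekept endpoint, and a failure there stops Tests 6-10, including the three quality-of-life tests. Sensitivity Analysis 2 is the main covariate-adjusted check on the primary result. In both, a recorded baseline variable that plausibly predicts outcome enters only in coarse form.

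The pointer to SAP 5.5 in the Test 5 section is also unclear. It may be left over, or the count may have been meant as a covariate. Two programmers could read it differently.

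**Working it through.** **1. The plan's own power figure.** Inputs (Protocol 8.1, SAP 3.2): two-sided Fisher test, alpha 0.05. Exact enumeration gives 99.9% for 96:64 at 35% vs 5%, and 99.9% for 72:48 at 56% vs 13%. The stated figure of at least 90% holds in both cases.

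**2. The 70% floor.** Largest 1-unit group = 0.30 x N.

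| N | Source | Most with 1 unit | Fewest with 2-4 units |
|---|---|---|---|
| 160 | Protocol 8.1 | 48 | 112 |
| 140 | SAP 17 | 42 | 98 |
| 120 | SAP 3.2 | 36 | 84 |

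**3. How much of the count the split keeps.** R-squared = between-level variance / total variance. The documents do not give the distribution of counts, so it is assumed.
- 30% at 1 unit, the rest equal over 2, 3 and 4: mean = 0.3 x 1 + 0.7 x 3 = 2.4. Between = 0.3 x 1.4² + 0.7 x 0.6² = 0.84. Total = 1.307. R-squared = 0.64.
- 10/30/30/30%: mean = 2.8. Between = 0.1 x 1.8² + 0.9 x 0.2² = 0.36. Total = 0.96. R-squared = 0.38.
- Over eight assumed distributions the range is 0.38 to 0.77, so the split misses about 23% to 62% of the variance. This treats the count as a whole number from 1 to 4; averaging over 16 weeks can give half units.

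**4. Test 5 with and without the count (simulation, 140 patients, 3:2).** Information ratio = (mean Z with count / mean Z without)². The transfusion process is assumed throughout.
- Gamma renewal process (interval shape 4, 9 or 25; 0-30% two-unit sessions; true rate uniform on 0.75-4.5 units per 8 weeks; 250 trials per scenario): 1% to 18% more information.
- Gamma-mixed Poisson process (600-1,000 trials per scenario): power changes of -0.7 to +2.5 points, for example 80.7% to 80.0% and 73.4% to 75.9%.
- A further simulation of the stratified rank procedure at 84 vs 56: about 4% to 10% more information and 0 to 5 points of power, with about 4% more information where placebo response was 13%.

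**5. Logistic model.** The renewal process gave +1 to +7 points and the mixed Poisson process -0.6 to +6.7 (for example 60.2% to 66.9%). Three cautions apply:
- The mixed Poisson runs put the count in place of the split. Adding it beside the split, as proposed below, costs one more parameter; a rerun gave smaller gains than the swap at the top of the range.
- The largest mixed Poisson gain came with 10% of patients in the 1-unit group. There, all 1-unit patients reached transfusion independence in many simulated trials, so the two-level coefficient could not be estimated. Part of that gain is a fitting problem, not precision.
- The adjusted log odds ratio also moves away from zero (0.91 to 0.96 in that scenario), as expected when a prognostic covariate is added to a logistic model.

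**6. Validity.** With no treatment effect, rejection rates in the mixed Poisson runs were 3.8% to 5.4% over both tests, with or without the count.

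**7. At the planned effect.** With 84 vs 56, 56% vs 13% responders, zero weeks for non-responders and an assumed uniform 8-28 weeks for responders, an unadjusted Wilcoxon test already has power above 99.9%. At 35% vs 5% it is above 99%. It drops below 90% only when the effect shrinks, for example 35% vs 13%.

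**Limits.** The mixed Poisson runs left out baseline Hb, EPO and IPSS-R; Hb is already in both models and may absorb part of the gain. Their simulated placebo response was 17% to 69%, against the SAP's 13%.

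**The case against.** The strongest reply is that this is a preference about precision. Protocol 8.3.3.2.2 calls for a non-parametric ANCOVA controlling for the stratification factors; the SAP does that and adds baseline Hb. Adjusting for the randomization factors is a valid, pre-specified choice, and any omitted covariate leaves some chance imbalance. Baseline burden is also tabulated by arm (SAP 8), and the primary endpoint is analysed by burden subgroup (SAP 12.4). All of this stands, and it is why the point is optional.

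Test 5 is reached only after Tests 1-4 succeed, when the effect is probably clear, and Sensitivity Analysis 2 is not confirmatory. Both points limit the value of extra power.

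The comparison with Test 6 is imperfect. Test 6 analyses change from baseline in pRBC/8 weeks, so its own baseline is the natural covariate, and there the count replaces the burden stratum. A reader might infer that the SAP contradicts itself by treating the two tests differently; it does not. Test 6 shows only that the count is available and usable.

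Replacing the two-level factor with the count in the logistic model would drop a randomization factor, impose linearity on the logit scale and move the model away from the CMH strata. That objection is right, and the fix below keeps the factor.

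What the objections do not remove is that the count is already derived, costs nothing to add, and is pointed to in the Test 5 section without being used.

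**Conclusion.** The point holds as an optional improvement. At least 70% of patients share one burden level in Test 5 and in Sensitivity Analysis 2, while a finer baseline measure exists for everyone. The expected gain is small: roughly 0-18% more information or -1 to +5 power points for Test 5, and -1 to +7 points for the logistic model, with the top of the latter range overstated for the reasons given. It is close to nil at 56% vs 13%. These figures rest on assumed count distributions and transfusion processes; only the 70% floor follows from the documents.

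A reader might infer that the Test 5 or primary result would be biased, or its type I error inflated. The documents do not support this: randomization is stratified on the same split, and simulated error stayed near 5%. Nor does the point reach the primary CMH test, which needs categorical strata and is adequately powered at the planned rates.

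**What to change.** Before the Week 28 unblinding:

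1. **SAP 12.3.3.3 (Test 5).** Name the within-stratum rank of baseline pRBC/8 weeks (SAP 5.5) as a second covariate beside the rank of baseline Hb, and keep all three stratification factors. This also gives the existing pointer to SAP 5.5 a purpose. If the sponsor does not want the covariate, delete the pointer.
2. **SAP 12.3.1.1, Sensitivity Analysis 2.** Add baseline pRBC/8 weeks as a continuous covariate alongside the 1 vs 2-4 factor, not in place of it. Make the same addition in the Appendix 19.7 calculation, which is required to match this model.
3. **Primary CMH test.** No change.

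Cost: about one line in each section and one extra model term. No new data, no change to the testing order and no effect on the primary test. Made after unblinding, the change would lose its credibility as pre-specified.
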